4.1.2 Statistical testing

While the primary and secondary objectives are defined based on the comparison between the pooled anifrolumab and placebo groups, the respective endpoints will also be tested for the individual anifrolumab regimens. The following hierarchical testing strategy (presented in [Figure 1](#)) will be used to provide strong control of the familywise error rate (FWER). As described in [Section 5](#), if the interim analysis is performed, some alpha will be spent, and the alpha at final analysis will be calculated based on a Peto-Haybittle spending function and the number of subjects at each analysis. The description below assumes that a two-sided alpha of 0.0499 is being used at the final analysis. If the interim analysis is not performed, the hierarchical testing strategy at the final analysis will use a two-sided alpha of 0.05.

Figure 1 Multiplicity correction at final analysis

- Step 1: The pooled anifrolumab regimens will be tested versus placebo at a 2-sided 4.99% significance level with regards to 24-hour UPCR (primary endpoint).
- Step 2: If the null hypothesis is rejected at Step 1, then the pooled anifrolumab regimens will be tested versus placebo at a 2-sided 4.99% significance level with regards to CRR (secondary endpoint).
- Step 3: If the null hypothesis is rejected at Step 2, then both anifrolumab regimens are individually tested against placebo, each at 2.50% significance level, for both endpoints (24-hour UPCR and CRR). If both regimens can be rejected for either endpoint, then alpha can be recycled and both regimens can be tested at 4.99% significance level for the remaining endpoint.

At Steps 1 and 2, strong control is due to the sequence testing. At Step 3, alpha is controlled given that the pooled hypothesis is tested first and if false, the two hypotheses corresponding to the two regimens for that endpoint cannot both be true.

4.1.3 Presentation of results

All analyses will use SAS[®] version 9.3 or higher. Summary tables will be presented by treatment group, and will include a pooled group comprising of both anifrolumab regimens. Treatment groups will be presented in the following order: anifrolumab basic regimen, anifrolumab intensified regimen, all anifrolumab and placebo. For continuous endpoints, data only up to IP discontinuation will be analysed. If IP has not been reported as prematurely discontinued, available data up to and including Week 104 will be used for continuous endpoints analyses. Otherwise, the date of IP discontinuation will be determined as the date of last IP administration. However, all subjects who have an infusion of IP within the Week 48 analysis visit window will be determined to have completed treatment in the double-blind treatment period, and their Week 52 data will be included in the analyses. Additionally, subjects who are determined to have completed treatment and have a Week 52 visit will not be imputed as non-responders at Week 52 for discontinuation of IP. The treatment policy sensitivity analysis of 24-hour UPCR will be analysed using all available data. Data (including derived variables) will be presented in listings sorted by treatment group and subject number.

Unless otherwise noted, categorical data will be presented using counts and percentages with the denominator for percentages being the number of subjects in the analysis set by treatment group. Percentages will be rounded to one decimal place; except 100% which will be displayed without any decimal places. Percentages will not be displayed for zero counts.

Unless otherwise noted, continuous variables will be summarised using the number of observations (n), mean, standard deviation (SD), median, minimum, and maximum. The minimum and maximum values will be displayed to the same level of precision as the raw data, the mean and median to a further decimal place and the SD to two additional decimal places. Any CI's, CVs, geometric means and any quartile values will also be presented to one more decimal place than the raw data.

95% CIs will be presented for treatment comparisons. If a model is used to estimate the treatment difference, the corresponding CI according to the model will be presented. Otherwise, the unadjusted CI will be used. Nominal p-values may be presented for endpoints not included in the strategy for preserving the type I error rate, but these cannot be interpreted in terms of statistical significance. The presentation of p-values will be to four decimal places unless a p-value is less than 0.0001, in which case "<0.0001" will be displayed.

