5.1.2 Systemic Lupus Erythematosus Disease Activity Index 2000

The SLEDAI-2K index (see [Appendix F](#)) consists of a list of organ manifestations, each with a definition. A certified Investigator or designated physician will complete the SLEDAI 2K assessment and decide whether each manifestation is "present" or "absent" in the last 30 days. The assessment also includes the collection of whole blood for analysis of C3, and C4 complement levels, and anti-dsDNA antibodies.

The proteinuria descriptor should be scored using the spot UPCR.

The SLEDAI-2K assessment consists of 24 lupus-related items. It is a weighted instrument, in which descriptors are multiplied by a particular organ's "weight". For example, renal descriptors are multiplied by 4 and central nervous descriptors by 8 and these weighted organ manifestations are totalled into the final score. The SLEDAI-2K score range is 0 to 105 points with 0 indicating inactive disease. The SLEDAI-2K scores are valid, reliable, and sensitive clinical assessments of lupus disease activity. The SLEDAI-2K calculated using a timeframe of 30 days prior to a visit for clinical and laboratory values has been shown to be similar to the SLEDAI-2K with a 10-day window ([Touma et al, 2010](#)). A timeframe of 30 days will be used in this study.

Any missing SLEDAI-2K laboratory assessments should be repeated.

5.1.3 Systemic Lupus International Collaborating Clinics/American College Rheumatology damage index

The SDI ([Appendix N](#)) has been developed to assess irreversible damage in SLE subjects independently of its cause (ie, included damage due to SLE activity, SLE-related scarring, therapy, comorbidities) but occurring after disease onset. Damage, ie, irreversible impairment since onset of SLE, is usually defined as a clinical feature that has to be continuously present for at least 6 months to score. In addition some irreversible events such as myocardial infarction or a cerebrovascular accident score as damage on their occurrence. Briefly, damage is defined for 12 organ systems; peripheral vascular, ocular, neuropsychiatric, renal, pulmonary, cardiovascular, gastrointestinal, musculoskeletal, skin, endocrine (diabetes), gonadal, and malignancies. Damage over time can be stable or increase, theoretically to a maximum of 47 points ([Schwartz et al, 2009](#)).

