
20 Mar 2019 Version 4.0
	
SAP to include updates to the restricted medications, non-responder rules and the interim analysis.
 
Interim analysis
 
Text was added to explain that the possible interim analysis will be either efficacy or futility, dependent on the results of a pivotal Phase 3 SLE study in anifrolumab. Non-binding stopping rules for the possible futility analysis have been included.
 
Changes to statistical analysis
 
The method used to manage strata with low counts for the CMH analyses has been clarified and updated.
 
MedImmune will no longer be calculating the type I IFN 21-gene signature parameters. Instructions on how to calculate these have been added to the SAP
 
Other changes
 
Medication beyond the protocol-allowed threshold and responder/non-responder criteria have been clarified in separate appendices (Appendix A and Appendix B, respectively).
 
P-values will be presented to 4 decimal places.
 
The estimand for all continuous endpoints (including the primary endpoint) is changing to the “while on treatment strategy” from the “treatment policy strategy”. The “while on treatment strategy” uses data up to Investigational Product (IP) discontinuation. The “treatment policy strategy” uses all collected data, irrespective of whether a subject discontinued IP or not. This change aims to deal with the risk of bias due to rescue medications after IP discontinuation. The sensitivity analysis will be changed to follow the “treatment policy strategy”.
 
The definition of oral corticosteroids at baseline has been updated.
 
OCS subgroup thresholds have been changed from (≤ 20 mg/day, > 20 mg/day) to (< 20 mg/day, ≥ 20 mg/day)

Date	Brief description of change

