4 ANALYSIS METHODS

4.1 General principles

4.1.1 Visit windows

For visit based analyses, the variables will be summarised based on the scheduled days with adjusted analysis-defined visit windows. The adjusted analysis-defined windows are summarised below:

Table 2 Visit windows

Adjusted Defined Windows Visit	Scheduled Study Day	Maximum Windows
Day 1	1	Study Day 1
Week 4	29	$2 \leq \text{Study Day} \leq 42$
Week 8	57	$43 \leq \text{Study Day} \leq 70$
Week 12	85	$71 \leq \text{Study Day} \leq 98$
Week 16	113	$99 \leq \text{Study Day} \leq 126$
Week 20	141	$127 \leq \text{Study Day} \leq 154$
Week 24	169	$155 \leq \text{Study Day} \leq 182$
Week 28	197	$183 \leq \text{Study Day} \leq 210$

Adjusted Defined Windows Visit	Scheduled Study Day	Maximum Windows
Week 32	225	211 ≤ Study Day ≤ 238
Week 36	253	239 ≤ Study Day ≤ 266
Week 40	281	267 ≤ Study Day ≤ 294
Week 44	309	295 ≤ Study Day ≤ 322
Week 48	337	323 ≤ Study Day ≤ 350
Week 52	365	351 ≤ Study Day ≤ 378
Week 56	393	379 ≤ Study Day ≤ 406
Week 60	421	407 ≤ Study Day ≤ 434
Week 64	449	435 ≤ Study Day ≤ 462
Week 68	477	463 ≤ Study Day ≤ 490
Week 72	505	491 ≤ Study Day ≤ 518
Week 76	533	519 ≤ Study Day ≤ 546
Week 80	561	547 ≤ Study Day ≤ 574
Week 84	589	575 ≤ Study Day ≤ 602
Week 88	617	603 ≤ Study Day ≤ 630
Week 92	645	631 ≤ Study Day ≤ 658
Week 96	673	659 ≤ Study Day ≤ 686
Week 100	701	687 ≤ Study Day ≤ 714
Week 104	729	715 ≤ Study Day ≤ 742
Week 108	756	743 ≤ Study Day ≤ 770
Week 112	784	771 ≤ Study Day ≤ 798

For assignment of data to time points using the visit windows, study day will be defined as (Date of assessment – date of first administration of IP) +1. Using this definition, the day of first dose of IP will be Day 1 and the scheduled visit date of Week 4 will be study day 29 (=28+1) for example.

If multiple readings are recorded within a single visit window, the following rules will be followed.

- If there are two or more observations within the same visit window, then the non-missing one closest to the scheduled visit will be used in the analysis.
- If two observations are equidistant from the scheduled visit, then the non-missing observation with the earlier collection date will be used in the analysis.
- If two observations are collected on the same day, then the non-missing one with the earlier collection time will be included in the analysis.

[figure not shown]
If a visit window does not contain any observations, then the data will remain missing.

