4.2 Analysis methods

4.2.1 Analysis of the primary variable

The primary estimand is evaluating the efficacy on disease activity of the pooled anifrolumab groups relative to placebo in subjects with active proliferative LN. This is measured by the

relative difference in change from baseline to Week 52 in the 24-hour UPCR. The full analysis set (as defined in Section 2.1.2) will be used, and any data collected after IP discontinuation will be excluded from the analysis, in order to reflect the effect of the initially assigned and dosed IP (anifrolumab or placebo), prior to the occurrence of the intercurrent event of IP discontinuation, applying a “while on treatment” estimand strategy. The individual anifrolumab regimens will also be assessed but not as part of the primary analysis.

The estimand for all continuous endpoints (including the primary endpoint) follows the “while on treatment” strategy, which includes data only up to IP discontinuation. If IP has not been reported as prematurely discontinued, available data up to and including Week 104 will be used for continuous endpoints analyses. Otherwise, the date of IP discontinuation will be determined as the date of last IP administration. However, all subjects who have an infusion of IP within the Week 48 analysis visit window will be determined to have completed treatment in the double-blind treatment period, and their Week 52 data will be included in the analyses.

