4.2.3.13 SLICC/ACR Damage Index

Change from baseline in SDI will be evaluated using the same analysis approach and summaries (except that SDI data will not be log-transformed) as specified in Section 4.2.3.5, with the appropriate substitution for the baseline value. SDI will also be analysed by baseline SDI (≥ 1 vs 0).

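### The on-treatment data cut also applies to SDI, so persistent new damage in subjects who stop IP before the Week 48 window cannot enter the SDI analysis

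*SAP*

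**What the plan says.** SAP 4.1.3: "For continuous endpoints, data only up to IP discontinuation will be analysed". For a subject reported as stopping early, "the date of IP discontinuation will be determined as the date of last IP administration". There is one exception: "all subjects who have an infusion of IP within the Week 48 analysis visit window" are treated as having completed the first year and keep their Week 52 values. SAP 4.1.1 sets that window at "323 ≤ Study Day ≤ 350". Subjects not reported as stopping early are used to Week 104. SAP 4.2.1 repeats the rule: "The estimand for all continuous endpoints (including the primary endpoint) follows the" while-on-treatment strategy. The SAP amendment history (version 4.0) gives the reason: "This change aims to deal with the risk of bias due to rescue medications after IP discontinuation".

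SDI falls under this rule. Protocol 8.5.3 names it among the continuous endpoints analysed by MMRM. SAP 4.2.3.13 says "Change from baseline in SDI will be evaluated using the same analysis approach" as in SAP 4.2.3.5, without log transformation. Section 4.2.3.5 is blacked out; in the readable text there is no exemption for SDI. The only treatment-policy analysis in the readable text is for 24-hour UPCR (SAP 4.1.3 and 4.2.1).

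SAP 3.3.17 describes SDI as the measure of irreversible damage, says it cannot fall below baseline, and provides for a listing by organ system. Protocol 5.1.3 says damage is usually "a clinical feature that has to be continuously present for at least 6 months to score", while some events, such as myocardial infarction, score when they occur.

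**The concern.** The cut was introduced for endpoints that rescue treatment can move in either direction. Applied to a slow, one-way index with few visits, it removes most of the period in which new damage could be recorded in a subject who stops early. Protocol 3.9.1 and 3.9.2 require IP to be stopped for a confirmed fall in eGFR, confirmed nephrotic-range proteinuria, or lupus activity needing prohibited immunosuppression, and SDI has a renal domain. Some of the excluded subjects are therefore plausibly at higher risk of damage. The MMRM then relies on subjects still on IP for what happened later. If stopping rates differ between arms, a difference in damage could be pulled towards zero.

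**Working it through.** The plan states no SDI figure to reproduce. The check applies the SAP rule to the visit schedule.

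**Inputs.** Post-baseline SDI visits are Weeks 24 and 52 (Protocol Table 2) and Weeks 80 and 104 (Protocol Table 4). Scheduled days, from SAP Table 2, are 169, 365, 561 and 729. The Week 24 window is Days 155-182 and the Week 48 window is Days 323-350. Infusions are every 4 weeks, so week w falls on day 7w + 1.

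**Step 1: visits kept for a premature stopper.** Keep an SDI visit if its day is on or before the last infusion day; add Week 52 if the last infusion is on Days 323-350.

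| Last infusion | Day | Post-baseline SDI kept |
|---|---|---|
| Weeks 0-20 | 1-141 | none |
| Weeks 24-44 | 169-309 | Week 24 |
| Week 48 | 337 | Weeks 24, 52 |
| Weeks 52-76 | 365-533 | Weeks 24, 52 |
| Week 80 or later | 561 onwards | Weeks 24, 52, 80 |

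The component-level LOCF rule in SAP 4.1.4.2 does not restore an excluded visit, because it needs at least 50% of the components.

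**Step 2: earliest scoring of persistent damage.** Six months is 365.25/2, about 183 days. Damage starting on Day 1 reaches six months on about Day 1 + 183 = Day 184. The Week 24 visit is Day 169 and its window closes on Day 182, so Week 52 is the first scheduled visit where such damage can score. A premature stopper last infused before Day 323 has no Week 52 value in the analysis. Only damage from events that score at once, recorded by Week 24 and on or before the last infusion, or features already present before Day 1, can count.

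**Step 3: size, on assumed rates.** The documents give neither stopping rates nor SDI accrual. Let s be the proportion stopping before the Week 48 window, a the proportion of stoppers gaining one SDI point by Week 52, and b the same in the rest. The mean change over everyone is s·a + (1 − s)·b. The on-IP analysis shows about b, taking stoppers to contribute no scored change and the model to project from the rest.

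With s = 20% and b = 2%:

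- a = 10%: 0.2 × 0.10 + 0.8 × 0.02 = 0.036; loss (0.036 − 0.020)/0.036 = 44%.
- a = 4%: 0.2 × 0.04 + 0.8 × 0.02 = 0.024; loss (0.024 − 0.020)/0.024 = 17%.
- a = 2%: 0.020; loss 0%.

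Between arms, with 25% stopping on placebo and 15% on anifrolumab, again with b = 2%:

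- a = 10%: 0.25 × 0.10 + 0.75 × 0.02 = 0.040 against 0.15 × 0.10 + 0.85 × 0.02 = 0.032, a difference of 0.008.
- a = 4%: 0.25 × 0.04 + 0.75 × 0.02 = 0.025 against 0.15 × 0.04 + 0.85 × 0.02 = 0.023, a difference of 0.002.
- a = 2%: no difference.

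In each case the on-IP analysis shows about 0.02 in both arms.

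**The case against.** The strongest defence is that a while-on-treatment strategy is a documented choice with a stated reason. A reader might infer that this reason cannot reach SDI because damage is irreversible. The documents do not support that. Protocol 5.1.3 counts damage whatever its cause, including therapy, so rescue treatment can add or prevent later points. Post-stop SDI mixes the effects of IP and rescue. This stands, and it is why the on-IP analysis should be kept beside the new one.

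A reader might also infer that the data are deleted, or that all of them are already in hand. Neither holds. SDI values remain in listings. After IP stops, Protocol 4.2.2 asks for all assessments only if possible, and its minimum list omits SDI. The follow-up schedules in Protocol Tables 3 and 5 have no SDI either, so post-stop values may be incomplete.

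The six-month requirement limits any remedy too. To score at Week 52 (Day 365), persistent damage must have begun by about Day 365 − 183 = 182, whichever estimand is used. IP is also stopped for reasons unrelated to worsening, such as subject decision, pregnancy or an adverse event (Protocol 3.9.4). Some damage is visible elsewhere: malignancy and adjudicated MACE are tabulated as AESIs to 84 days after the last dose.

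None of this restores newly arising persistent damage in early stoppers to the SDI model or summaries.

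**Conclusion.** The point holds. On the readable text, persistent damage that begins after first dose in a premature stopper last infused before the Week 48 window cannot enter the SDI analysis. This rests on SDI following its schedule, on the usual six-month scoring rule, and on the blacked-out section containing no exemption.

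The exclusion is plausibly informative, but its size is unknown. A reader might take 44% as the expected loss, or conclude that the endpoint loses most of its information. The documents support neither: the loss runs from 0% to 44% over the assumed rates shown, depending on how much more damage stoppers accrue. Any pull towards no difference between arms likewise needs both unequal stopping rates and higher accrual in stoppers.

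SDI is exploratory, with nominal p-values and no formal testing (Protocol 8.5.3, SAP 4.1.3). The primary and secondary conclusions, alpha and power are unaffected. This is a worthwhile, low-cost improvement to a secondary line of evidence.

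**What to change.** In SAP 4.2.3.13, add an analysis of change in SDI to Week 52, and to Week 104 for subjects who entered the extension, on all collected values regardless of IP discontinuation. This mirrors the treatment-policy analysis already specified for 24-hour UPCR. Add the proportion with any SDI increase among subjects assessed, with the number assessed after stopping IP shown by arm. Report both next to the on-IP analysis.

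The cost is a short SAP addition, one extra model run and a simple table. The result must be read knowing that post-stop SDI may be incomplete and includes effects of rescue treatment.

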2.1.2 Full analysis set

The full analysis set will be used as the primary population for reporting efficacy and safety data. This comprises all subjects randomised into the study who receive at least one dose of IP and will be analysed according to randomised treatment (modified intent-to-treat [mITT] principle). Any major deviations from randomised treatment will be listed and considered when interpreting the safety data.

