3.6.7 Cushingoid features

Subjects will be assessed for Cushingoid features such as moon face, buffalo hump, purple or violaceous striae, central obesity, hirsutism, acne, easy bruising, and fragile skin which will be captured separately within the study eCRF to evaluate whether resolution of same can occur overtime with OCS reduction. These features will be presented by visit.

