4.1.4 Missing data

The study was designed to reduce the risk for missing data as much as possible through the following measures:

- From randomisation to Week 40, the study design allows for one burst and taper of corticosteroid for increased SLE disease activity or non-SLE causes.

- The dose of MMF may be increased up to 3 gm/day in case of suboptimal response.
- Subjects will receive IV methylprednisolone 500 mg on Week 0 (Day 1), prior to receiving the IP.
- Subjects may also receive up to one additional (optional) dose of IV methylprednisolone (≤ 500 mg) for renal or extra-renal disease activity between Week 0 (Day 1) visit and Week 8 visit. This optional dose can be given over two consecutive days.
- Subjects who require additional bursts of OCS will still be allowed to remain in the study, but will be considered non-responders for subsequent responder analyses (such as CRR).

Subjects who discontinue IP will be followed up and asked to come to each visit for the scheduled assessments through the Week 52 visit (or for a minimum of 12 weeks after last dose of IP for subjects for whom IP was discontinued within 12 weeks prior to Week 52).

The following measures will be applied to the second year extension period to also reduce the risk for missing data:

- From Week 52 to Week 92, the study design allows for one burst and taper of corticosteroid.
- Subjects who require additional bursts of OCS during the second year extension period will still be allowed to remain in the study, but may be considered non-responders for subsequent responder analyses (such as CRR at Week 104).

Subjects who discontinue IP in the second year extension period will be followed up until Week 104 (or for a minimum of 12 weeks after last dose of IP for subjects for whom IP was discontinued within 12 weeks prior to Week 104).

Missing safety data will generally not be imputed. However, safety assessment values of the form of $<x$ (i.e. below the lower limit of quantification) or $>x$ (i.e. above the upper limit of quantification) will be imputed as x in the calculation of summary statistics but displayed as $<x$ or $>x$ in the listings.

Details about imputation of partial or missing dates are given in [Appendix D](#). The imputation of single missing items for the derivation of a total score is described in [Appendix E](#).

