4.2.6 Analysis methods for safety variables

Safety variables will be summarised by treatment group for the full analysis set.

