4.2.6.2 Laboratory variables

Observed values and changes from baseline of laboratory data for haematology, clinical chemistry and fasting lipid profile will be summarised by visit. The summary statistics presented will be minimum, 1st quartile, median, 3rd quartile, maximum, mean, and SD.

Shift plots (scatter plots) for each of the parameters presenting baseline values versus minimum post-baseline values and maximum post-baseline values, respectively, will be provided. A diagonal line indicating no change and horizontal and vertical reference lines indicating the limits of the reference ranges will also be displayed on the shift plots.

If any laboratory variables show any unusual features (high or low values or a general shift in the data points) at specific visits, then shift plots of these data may also be produced. This will be discussed and agreed upon during the BDR meeting.

For each laboratory parameter with available criteria, the number and percentage of subjects with TELVC values will be summarised by visit. Additionally, the number and percentage of subjects with at least one TELVC value will be presented.

The number and percentage of subjects with laboratory values below, within or above the corresponding normal range will be presented by visit. Urinalysis will be summarised as shift tables from baseline to the last on-treatment value for each parameter. Furthermore, the number and percentage of subjects with treatment-emergent changes will be summarised by parameter. In addition, observed values and change from baseline and pre-specified categories will be summarised by visit for any continuous variables.

In order to identify potential Hy's Law cases, the number and percentage of subjects in categories based on multiples of ULN for maximum on-treatment ALT and AST by maximum total bilirubin will be presented in a table. The table will include the following categories: < and $\geq 2xULN$ for total bilirubin and < $3xULN$, $\geq 3 - < 5xULN$, $\geq 5 - < 10xULN$ and $\geq 10xULN$ for ALT/AST.

Individual subject data will be presented for all subjects who meet the criteria for potential Hy's law. The relevant laboratory parameters (ALT, AST, total bilirubin and ALP) will be tabulated showing all visits for these subjects. Subjects with elevated ALT or AST (ALT or AST $\geq 3 \times \text{ULN}$) and elevated total bilirubin ($\geq 2 \times \text{ULN}$) at any time during the study (not necessarily at the same time) will be included.

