4.2.6.6 Cushingoid features

The number and percentage of subjects will be summarised for each feature by visit and treatment group. For subjects with baseline OCS ≥ 10 mg/day prednisone or equivalent, the summary will be repeated by OCS status at Week 52 (target OCS dose of ≤ 7.5 mg/day

reached versus target OCS dose of ≤ 7.5 mg/day not reached) and at Week 104 (target OCS dose of ≤ 5.0 mg/day reached versus target OCS dose of ≤ 5.0 mg/day not reached).

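### By-visit categorical safety percentages are divided by the whole full analysis set, so they are diluted at later visits, chiefly after Week 60 and most seriously for Cushingoid features at Weeks 80 and 104

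*SAP*

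**What the plan says.** SAP 4.1.3 gives one default for categorical data, to apply unless something else is noted: "the denominator for percentages being the number of subjects in the analysis set by treatment group". SAP 4.2.6 names the set: "Safety variables will be summarised by treatment group for the full analysis set". SAP 2.1.2 defines it: "This comprises all subjects randomised into the study who receive at least one dose of IP". That number is fixed at the first dose and does not shrink over time.

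The by-visit categorical safety tables note no other denominator:

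- Cushingoid features (SAP 4.2.6.6): "The number and percentage of subjects will be summarised for each feature by visit and treatment group". SAP 3.6.7 gives the purpose: "to evaluate whether resolution of same can occur overtime with OCS reduction".
- Laboratory range categories (SAP 4.2.6.2): "The number and percentage of subjects with laboratory values below, within or above the corresponding normal range will be presented by visit".
- Laboratory TELVC (SAP 4.2.6.2): "the number and percentage of subjects with TELVC values will be summarised by visit".
- Vital-sign range categories and TELVC (SAP 4.2.6.5), in similar terms.

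SAP 4.1.4 adds: "Missing safety data will generally not be imputed". SAP 4.1.1 leaves an empty visit window missing.

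Elsewhere the SAP does narrow the denominator. Neutralising antibodies by visit use subjects with a non-missing ADA result at that visit (SAP 3.7.1). Follow-up adverse events use subjects with documentation in that period (SAP 4.2.6.1). Year 2 disposition uses Year 2 entrants (SAP 4.2.5.1).

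**The concern.** Under this rule a subject with no assessment at a visit is in effect counted as free of the feature or abnormality. The printed percentage is then the rate among those assessed, multiplied by the share of the arm that was assessed. As that share falls, the percentage falls, even if nobody changes.

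The loss after Week 52 is built into the design. Subjects who fail the Week 52 criteria (SAP 1.2.5) have their last visits at Weeks 56 and 60 (Protocol Table 3). Laboratory tests and vital signs continue every 4 weeks to Week 104, and Cushingoid features are assessed at Weeks 80 and 104 (Protocol Table 4). From Week 64 on, only Year 2 entrants can supply planned values, yet each count is divided by the full arm.

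For Cushingoid features, a fall that comes only from missing assessments would look like the resolution the table is meant to examine. A row for a single feature gives no sign of this.

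**Working it through.** The plan states no figure on this point: no expected attrition, no Year 2 entry rate, no feature or abnormality rate. There is nothing to reproduce, and the sizes below rest on assumptions shown as a range.

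**Inputs.** N = 50 per arm, from about 150 subjects randomised 1:1:1 (SAP 1.2). The true rate among assessed subjects, r, and the number assessed at the visit, m, are assumed.

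**Formula.** Printed % under SAP 4.1.3 = (r × m) / N. With a non-missing denominator it is (r × m) / m = r.

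**Constant true rate, r = 20%, N = 50:**

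| Share assessed | m | Count with feature | Printed, full set | Printed, non-missing |
|---|---|---|---|---|
| 90% | 45 | 9 | 9/50 = 18% | 9/45 = 20% |
| 80% | 40 | 8 | 8/50 = 16% | 8/40 = 20% |
| 70% | 35 | 7 | 7/50 = 14% | 7/35 = 20% |
| 60% | 30 | 6 | 6/50 = 12% | 6/30 = 20% |
| 50% | 25 | 5 | 5/50 = 10% | 5/25 = 20% |
| 40% | 20 | 4 | 4/50 = 8% | 4/20 = 20% |

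The dilution is proportional. At 50% assessed, true rates of 10% and 30% print as 5% and 15%. The pooled anifrolumab group (N = 100) gives the same percentages.

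**Between arms, r = 20% in both:**

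- Equal share assessed, 50% and 50%: 10% against 10%, no false difference, though both have fallen.
- Assumed 60% on anifrolumab and 40% on placebo: 0.20 × 0.60 = 12% against 0.20 × 0.40 = 8%, a false difference of 4 points.

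**Could entry differ by arm?** The planning assumptions in SAP 1.3 (Week 52 to baseline UPCR ratios of 0.35 and 0.54, SD 0.8 for the log change) allow a rough check. One entry criterion, for subjects with baseline UPCR above 3 mg/mg, is more than 50% improvement:

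- anifrolumab: Φ(ln(0.50/0.35)/0.8) = Φ(0.446) = 67%
- placebo: Φ(ln(0.50/0.54)/0.8) = Φ(−0.096) = 46%

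This is one criterion in one stratum and not an entry rate. It shows only that unequal entry is plausible if the drug works as planned, and that the false excess would then fall on anifrolumab.

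**The case against.** There is a fair case that this is minor.

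- *Laboratory and vital-sign tables carry other cues.* Observed values and changes are also summarised by visit, and the SAP 4.1.3 default for continuous data includes the number of observations (SAP 4.2.6.2 lists its statistics without repeating it). Low, normal and high will visibly add to less than 100%. Vital signs also get shift tables. A reader might infer that laboratory abnormality rates in general will appear to fall unnoticed; these displays do not support so broad a reading. This stands.
- *Year 1 is less exposed.* Subjects who stop IP are asked to keep attending to Week 52, with chemistry, haematology, urinalysis and vital signs in the minimum set (Protocol 4.2.2). This stands, although Cushingoid features are not in that minimum set.
- *There is a second Cushingoid table.* SAP 4.2.6.6 repeats the summary, for subjects with baseline OCS of at least 10 mg/day, by whether the OCS target was reached. It is closer to the stated question, but it gives no denominator of its own, so it does not settle the point.
- *Table shells might define n/N.* Shells and the SAP appendices were not available here. The SAP text seen does not define it, and its default applies unless something else is noted.
- *Nothing inferential depends on these tables.* They are descriptive, and counts are printed. This stands, and it limits the consequence.

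Two further inferences go beyond the documents. The narrower denominators used elsewhere might suggest that the default is an oversight; they show inconsistency, but nothing states intent. It might also seem that the adverse-event tables by onset interval need the same change. Those tables count first onsets, not status at a visit, and by default carry event rates per subject-year, so the argument here does not extend to them.

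**Conclusion.** The concern holds on the SAP text. By-visit categorical safety percentages are diluted by the share of the arm not assessed, chiefly after Week 60. The most affected display is Cushingoid features at Weeks 80 and 104. Laboratory and vital-sign tables are affected less seriously, because other summaries show how many were observed.

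The size cannot be fixed from the documents. The 18% to 8% range for a true 20% assumes a constant rate and 90% to 40% of the arm assessed. A difference between arms appears only if the share assessed differs by arm. A reader might infer that a printed fall means nobody improved; that cannot be presumed either, because Year 2 entrants are selected on renal response and must meet OCS limits to stay on IP. The table as specified cannot separate real improvement from missing assessments.

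**What to change.** In SAP 4.1.3, state that by-visit categorical safety tables (Cushingoid features, laboratory and vital-sign range categories, TELVC by visit) use as denominator the subjects with a non-missing assessment in that visit window, shown as n/N by treatment group.

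In SAP 4.2.6.6, report Cushingoid resolution among subjects who had the feature at baseline and are assessed at that visit.

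Add a caveat to the Year 2 tables that these visits describe subjects selected on Week 52 renal response. The new denominator removes dilution but not selection, so prevalence at Week 104 could still be below baseline without any change within subjects.

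The cost is a few SAP sentences and a small programming change. No new data are needed.
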